1.3 Masking

This is a post-approval, open-label study. Treatment is known to the investigators, subjects, and Alcon personnel involved with the planning and execution of the study.

1.4 Interim Analysis

Interim reports pertaining to the progress of the post-approval study will be submitted to the FDA for review every 6 months for the first two years, starting from the date of approval, and will continue to be submitted annually thereafter, until study completion.

For each interim report, the number of subjects enrolled and implanted with the CyPass device will be reported. In addition, the number of clinically relevant complications associated with CyPass Micro-Stent placement and stability (events toward the primary safety endpoint) will be reported, and a listing and summary table with the number of adverse events, and number and proportion of subjects experiencing all such events will be provided. A listing of all ocular SAEs will also be provided. A summary of the secondary effectiveness endpoints will be reported once 50% of the subjects in the intention to treat analysis set have completed Visit 5 (6 Month Follow-up Visit).

2 Analysis Sets

All subjects will be considered enrolled once they have signed the informed consent form.

2.1 Intention to Treat Analysis Set

The intention to treat (ITT) analysis set will be defined as the set of study eyes for which a CyPass Micro-Stent implant is attempted. The ITT analysis set will serve as the primary set for the safety and effectiveness summaries and analyses, as well as for all demographics, baseline, surgery, and study conduct summaries.

3 General Reporting Conventions

- ≠ All study eyes will receive the same treatment consisting of CyPass Micro-Stent implantation following uncomplicated cataract surgery. Therefore, summary tables will be presented for all subjects combined across all investigative centers.
- ≠ Available data at each assessment time point will be presented. No imputations will be made for missing data.
- ≠ Appropriate descriptive statistics will be computed and displayed (by assessment time point and other key variables as appropriate for both continuous and categorical variables as described below).

For continuous variables, descriptive statistics include n (number of subjects/eyes) with non-missing data, mean, standard deviation (SD), median, minimum and maximum values. The following number of decimal places will be used: mean and

median values to one more decimal place than the raw data; minimum, and maximum to the same number of decimal places as the raw data and SD to two more decimal places than the raw data.

For categorical parameters, the number and percentage of subjects/eyes within each category will be presented. The denominator for percentages will be based on the number of subjects/eyes with non-missing data appropriate for summary purposes. If a count of zero is obtained for categorical data, the zero count and percentage will still be displayed. Unless otherwise noted, percentages will be presented to one decimal place.

With the exception of the primary study endpoint, that is a one-sided test ($\alpha=0.05$), all other applicable confidence intervals (CI) will be at the $\alpha = 0.05$ (two-sided) level.

- ≠ Baseline is defined as the last assessments obtained prior to CyPass implantation surgery on Day 0.
- ≠ Change from baseline (pre-surgery) (where relevant) will only be summarized for subjects with both screening (pre-surgery) and post-op data for the relevant visit
- ≠ Study day: Study day will be calculated relative to the date of CyPass implantation surgery (Day 0) as: Date of event – date of surgery. This formula will be used when calculating days to a specific event (i.e., ocular medications and/or AE start date). A negative study day indicates an event prior to surgery.
- ≠ Individual listings of data represented on the eCRF will be provided to facilitate investigation of the tabulated values and to allow for clinical review of key variables. All data listings will be sorted by site-subject number, visit, and assessment time points where appropriate. Data from unscheduled visits will be excluded from the summary tables (except for adverse events) but included, chronologically, in the data listings.

4 Study Conduct, Subject Baseline, and Surgical Summaries

All summaries in this section will be presented for the ITT analysis set, unless otherwise specified.

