12.2 Study Visits

All subjects will participate in defined follow-up visits through 36 months. A follow-up electronic Case Report Form (eCRF) shall be completed for each scheduled exam.

Unscheduled visits must also be recorded using the appropriate eCRF.

Informed consent MUST be properly completed and documented prior to performing any study-specific testing. Upon signing informed consent, subjects are considered enrolled in the study. All subjects will be assigned a single subject identifier at the screening visit. The subject identifier consists of a combination of a 4-digit investigator number and a 5-digit subject number. The number is automatically generated sequentially by the electronic data capture (EDC) system. As an example: “1234.00001” (the investigator number and the subject number are separated by a “.” character). This number will be used throughout the clinical study.

It is recommended that ocular assessments be performed in the order presented below. All assessments must be recorded in source documentation, and also in the eCRF, if applicable.

Adverse events are collected and reported for both the study eye and the fellow eye (refer to Section 13 DEVICE DEFICIENCIES AND ADVERSE EVENTS).

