5. Measure IOP with Goldmann tonometer between 8:00 and 10:00 am.
6. Conduct slit lamp examination.
7. Perform Gonioscopy (including Shaffer grading for all 4 quadrants) with goniophotography of CyPass location.
8. Conduct dilated fundus examination (including C:D assessment).
9. Conduct central corneal pachymetry.
10. Record any adverse events and/or device deficiencies.

NOTE: SAEs must be entered into EDC within 24 hours of the Investigator's knowledge. Refer to Section 13 for further detail.

12.2.10 **36 Month Follow-up / Exit / Early Exit (Visit 8)**

Visit 8 must occur 1050-1140 days postoperatively. Below is a list of study procedures to be undertaken at this visit. Ocular assessments will be conducted for the study eye, unless otherwise noted.

1. Document changes in concomitant medications.
2. Perform manifest refraction and record monocular BCDVA using an ETDRS chart at 4 meters.
3. Perform a Humphrey 24-2 SITA standard visual field.
4. Perform specular microscopy. If requested by the sponsor, may also be performed in the fellow eye.
5. Measure IOP with Goldmann tonometer between 8:00 and 10:00 am.
6. Conduct slit lamp examination.
7. Perform Gonioscopy (including Shaffer grading for all 4 quadrants) with goniophotography of CyPass location.
8. Conduct dilated fundus examination (including C:D assessment).
9. Conduct central corneal pachymetry.
10. Record any adverse events and/or device deficiencies.

NOTE: SAEs must be entered into EDC within 24 hours of the Investigator's knowledge. Refer to Section 13 for further detail.

11. Exit the subject from the study after completion of this visit.

12.3 **Unscheduled Visits**

An unscheduled visit (USV) is defined as one that meets all of the following:

- ≠ Examination that is not required by the protocol
- ≠ Examination conducted by the study staff
- ≠ New finding, continuation of an existing finding, or a change to a previous finding is noted in the study eye

An USV may or may not result in the capture of an adverse event. Likewise, an AE may be captured without the report of an USV (eg, AE identified subsequent to study eye examination by non-study personnel).

The assessments captured at the USV are dictated by the Investigator per his/her medical judgment. The following assessments/documentation are recommended:

- ≠ Concomitant medications
- ≠ Manifest refraction and BCDVA
- ≠ Specular microscopy (study eye or fellow eye)
- ≠ IOP
- ≠ Slit lamp examination
- ≠ Gonioscopy

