6.4 Other Safety Outcomes

The following safety outcomes will be summarized by numerator (number of eyes experiencing the outcome), denominator (number of eyes in the ITT set), and the rate of ITT eyes experiencing the outcome.

≠ Increase from baseline IOP of 10 mmHg or greater at any time at/after 30 days postoperative

- Change in IOP from baseline at/after 30 days postoperative is defined as,

$$Change = PostOp IOP - Baseline IOP$$

- Note: for subjects having IOP change ≥ 10 mmHg at any time at/after 30 days postoperative, a subject will be counted only once for reporting this outcome across all postoperative visits..

- # BCDVA loss of 2 or more lines compared to screening (Visit 0)
 - Change in BCDVA from screening to any postoperative visit is defined as,

$$Change = PostOp BCDVA - Screening BCDVA$$

- # BCDVA loss of 2 or more lines in comparison with best recorded BCDVA at any postoperative visit.

Note: for subjects with BCDVA loss of 2 or more lines to any visit, a subject will be counted only once for reporting this worsening across all postoperative assessments.

- # Device movement, defined as a change by at least 1 in the number of CyPass rings visible (e.g., from 1 ring to 2 rings or from 3 rings to 2 rings) that does not result in clinical sequelae (e.g., secondary surgical intervention to modify device position, corneal endothelial touch by device, corneal edema leading to loss of BCDVA > 2 lines at the last postoperative visit in comparison with preoperative BCDVA, progressive endothelial cell loss, erosion of device through sclera, or device obstruction requiring secondary surgical intervention), and that is not attributable to any one or more of the following:
 - o variations in gonioscopic viewing angle or illumination
 - o changes in angle anatomy due to concomitant findings such as resolution of hyphema
 - o changes in anterior chamber depth
 - o development of focal peripheral anterior synechiae

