The rate of ocular SSIs associated with CyPass placement and stability	Adverse Event(s) SX	
Either of these two:
 
Postop - ee) CyPass device explantation associated with CyPass placement and stability
 
Postop - gg) Unplanned ocular surgical reintervention associated with CyPass placement and stability

Other Safety Endpoints		
Increase from baseline IOP of 10 mmHg or greater at any time at/after 30 days postoperative	Baseline: Intraocular Pressure_Glaucoma PostOp: Intraocular Pressure_Glaucoma_1	
BCDVA loss of 2 or more lines compared to screening (Visit 0)	Baseline: Visual Acuity_VAS PostOp: Visual Acuity_VAS_1	
BCDVA loss of 2 or more lines in comparison with best recorded BCDVA at any postoperative visit	Baseline: Visual Acuity_VAS PostOp: Visual Acuity_VAS_1	

Endpoint	CRF	Comments
Device movement, defined as a change by at least 1 in the number of CyPass rings visible (eg, from 1 ring to 2 rings or from 3 rings to 2 rings) that does not result in clinical sequelae (eg, secondary surgical intervention to modify device position, corneal endothelial touch by device, corneal edema leading to loss of BCDVA > 2 lines at the last postoperative visit in comparison with preoperative BCDVA, progressive endothelial cell loss, erosion of device through sclera, or device obstruction requiring secondary surgical intervention), and that is not attributable to any one or more of the following:	Adverse Event(s) SX	Postop - dd) CyPass device dislodgement or movement, without sequelae (as defined in the protocol)
variations in gonioscopic viewing angle or illumination		
changes in angle anatomy due to concomitant findings such as resolution of hyphema		
changes in anterior chamber depth		
development of focal peripheral anterior synechiae		

Endpoint	CRF	Comments
Additional Safety Assessments		
Adverse events (ocular and non-ocular)	Adverse Event(s) SX	
Device deficiencies	Device Deficiency	
Endothelial Cell Count	This will come from a dataset provided by the reading center, CIARC	
Slit lamp findings	Baseline: Slit Lamp Observations PostOp: Slit Lamp Observations_1	
Fundus examination (C/D ratio) and fundus findings	Baseline C/D: Fundus Exam PostOp C/D: Fundus Exam_1 Baseline observations: Fundus Observations PostOp observations: Fundus Observations_1	
Corneal pachymetry	Baseline: Corneal Thickness PostOp: Corneal Thickness_1	
Intraocular pressure	Baseline: Intraocular Pressure_Glaucoma PostOp: Intraocular Pressure_Glaucoma_1	

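### The any-time IOP-rise rate in SAP 6.4 counts an eye as event-free if its rise was measured only at an unscheduled visit

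*SAP*

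**What the plan says.** SAP Section 3 (General Reporting Conventions) sets the rule for off-schedule data: "Data from unscheduled visits will be excluded from the summary tables (except for adverse events". The sentence goes on to keep those data in the listings. No other exception is named, and the same section rules out imputation.

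SAP 6.4 lists this outcome: "Increase from baseline IOP of 10 mmHg or greater at any time at/after 30 days postoperative". It is to be summarised by "numerator (number of eyes experiencing the outcome), denominator (number of eyes in the ITT set), and the rate of ITT eyes experiencing the outcome". A note adds that a subject with more than one such rise counts once over the postoperative visits.

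SAP Appendix C gives the source of the outcome as "Baseline: Intraocular Pressure_Glaucoma PostOp: Intraocular Pressure_Glaucoma_1", that is, the IOP forms. Device movement, another SAP 6.4 outcome, comes instead from the adverse event form: "Postop - dd) CyPass device dislodgement or movement, without sequelae (as defined in the protocol".

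Protocol 12.2 says: "Unscheduled visits must also be recorded using the appropriate eCRF". Protocol 12.3 defines an unscheduled visit by three conditions that must all hold. One is "New finding, continuation of an existing finding, or a change to a previous finding is noted in the study eye". On content it says "The assessments captured at the USV are dictated by the Investigator per his/her medical judgment", and IOP is among the recommended assessments.

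**The concern.** The definition covers any time from day 30, but the reporting convention removes every reading taken outside the schedule. Because the denominator is all ITT eyes rather than eyes with a reading, a removed rise is not treated as missing. It is counted as no rise.

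The removed readings are not a neutral subset. By the protocol's definition, an unscheduled visit is one at which something was found in the study eye, so these are visits where a pressure rise is more likely to be seen.

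Scheduled readings are also sparse late in follow-up. A rise that comes and goes between two annual visits can be measured only off schedule. At stake is a prespecified safety rate that would read as more favourable than the recorded data support.

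**Working it through.** The documents give no expected rate for this outcome, so there is no plan figure to reproduce. The check has three parts.

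**1. The rules applied to one eye.** Take an ITT eye with a rise of at least 10 mmHg after day 30, measured only at an unscheduled visit.
- SAP 3: the reading is excluded from summary tables unless it is adverse-event data.
- Appendix C: this outcome is IOP-form data, so the exception does not apply.
- SAP 6.4: the eye is in the denominator because it is in the ITT set.

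It adds 0 to the numerator and 1 to the denominator. No rule acts in the opposite direction, so the bias is only downward.

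**2. Gaps between scheduled readings** (visit windows in Protocol 6 and 12.2).
- Visit 5 to 6: 330 − 210 = 120 to 420 − 150 = 270 days.
- Visit 6 to 7: 690 − 420 = 270 to 780 − 330 = 450 days.
- Visit 7 to 8: 1050 − 780 = 270 to 1140 − 690 = 450 days.

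**3. Illustration of size.** Only the windows come from the documents; durations, onset patterns, capture chances and rates are assumed.

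Window midpoints for Visits 4 to 8 are days 84, 180, 375, 735 and 1095. Visit 3 has midpoint 28 and is left out. A Visit 3 reading on days 30 to 35 would count, so scheduled capture of the earliest rises is slightly understated. Gaps from day 30 are 54, 96, 195, 360 and 360 days, in total 1065.

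For one rise per eye with uniform onset and duration D, the chance that it overlaps a scheduled reading is s = Σ min(D, gap) / total.
- Onset over days 30 to 1095: D = 30 gives 150/1065 = 0.141; D = 90 gives (54 + 4×90)/1065 = 0.389; D = 180 gives (54 + 96 + 3×180)/1065 = 0.648; D = 360 gives 1.
- Onset over days 30 to 180: D = 30 gives 60/150 = 0.40; D = 90 gives (54 + 90)/150 = 0.96; D = 180 gives 1.

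A simulation of 400,000 onsets for D = 30, 90 and 180 gave 0.141, 0.389 and 0.648 (even onset) and 0.399, 0.959 and 1.0 (early onset).

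If a share u of the rises missed on schedule is measured at an unscheduled visit, the table drops (1 − s)u / [s + (1 − s)u] of all measured rises:

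| Assumed rise | s | u = 10% | u = 30% | u = 60% |
|---|---|---|---|---|
| 30 days, even onset | 0.141 | 38% | 65% | 79% |
| 30 days, early onset | 0.40 | 13% | 31% | 47% |
| 90 days, even onset | 0.389 | 14% | 32% | 49% |
| 90 days, early onset | 0.96 | 0.4% | 1.2% | 2.4% |
| Lasts to next scheduled visit | 1 | 0% | 0% | 0% |

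The reported rate is r(1 − d), where r is the share of eyes with a measured rise and d the share of those seen only off schedule. With the 450 eyes targeted for implantation and d = 10%, 30%, 60%:
- r = 3%: 2.7%, 2.1%, 1.2%.
- r = 5%: 4.5%, 3.5%, 2.0%, that is 20.2, 15.7 and 9.0 eyes against 22.5.
- r = 8%: 7.2%, 5.6%, 3.2%.

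**The case against.** The strongest reply is that a specific definition prevails over a general convention. SAP 6.4 covers any time from day 30 and counts once over postoperative visits, and Appendix C does not limit the IOP form to scheduled visits. But neither place mentions unscheduled visits, while SAP 3 names its single exception and this outcome is not in it. At best, two programmers could report different rates from the same SAP.

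Second, Protocol 13.1.2 item z lists nearly the same rise as an anticipated adverse event. Protocol 15.5.4 asks for event rates for postoperative ocular adverse events in study eyes, and SAP 3 keeps unscheduled adverse events in the tables. This stands in part: a rise reported that way is not lost from the report. It still has to be reported as an adverse event. Protocol 13.3 leaves that decision to the investigator and names raised IOP among early findings that may not qualify, although item z starts at 1 month and has a numeric threshold, which narrows the discretion. SAP 6.5.1 tabulates by MedDRA class and preferred term, not by the 10 mmHg threshold. The listings show the readings but give no rate.

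Third, scheduled-only tabulation is defensible, because unscheduled readings are discretionary and depend on how often an eye is seen. That is a fair argument for an outcome labelled as scheduled-only. This one is defined as occurring at any time.

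Finally, the illustrated loss runs from 0% to 79% and cannot fix the true size. That stands.

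**Conclusion.** The concern holds. Under the SAP's stated rules, an eye whose rise was measured only at an unscheduled visit is reported as event-free, and the SAP 6.4 rate is too low whenever such eyes exist. The direction is certain; the size is not. It depends on how long rises last, when they start and how often they are measured off schedule, none of which the documents give. It could be negligible if rises persist and substantial if they are short and spread over follow-up.

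The scope is limited to one descriptive outcome without a hypothesis. The primary endpoint, its power and the safety endpoints taken from the adverse event form are unaffected. A prespecified safety rate with a one-sided error that is cheap to remove should still be corrected before database lock.

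**What to change.** - **SAP 3:** name the any-time IOP-rise outcome beside adverse events as an exception to the exclusion.
- **SAP 6.4:** state that it is derived from all study-eye IOP readings at or after day 30, scheduled or unscheduled. Report separately the number of eyes that enter through unscheduled readings alone, so that the scheduled-only rate can still be read off.
- **By-visit IOP summaries:** these can keep the scheduled-only rule.

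The cost is SAP wording and programming. No new data are needed, since the protocol already requires unscheduled visits to be recorded on an eCRF. The drawback is less uniform ascertainment across eyes and sites: unscheduled readings are discretionary, more frequent in eyes with problems and not tied to the 8 to 10 am window. The separate count keeps this visible.

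Whether unscheduled acuity counts in the two BCDVA-loss outcomes of SAP 6.4 is a separate wording point, not covered here.

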4.1 Subject Disposition

A subject disposition table will be presented that displays the number of subjects enrolled in addition to the number of screen failures as well as the number subjects treated, completed, and discontinued. This table will also contain counts for each reason for premature study discontinuation. Furthermore a listing of reasons for early study discontinuation will also be provided.

An accountability table as per ANSI Z80.27-2014 (revision of ANSI Z80.27-2001 (R2011)), Annex G will be provided.

4.2 Protocol Deviations

A listing of protocol deviations will be provided.

4.3 Demographic and Baseline Characteristics

Subject demographics to be summarized include age, sex, race, and ethnicity. Baseline summaries will include study eye (OD, OS) and baseline IOP .

4.4 General Medical and Ophthalmic History

All general medical history and ophthalmic history findings will be presented in separate data listings.

4.5 Implantation Surgery

CyPass implantation information regarding the placement of the device and surgical procedural data will be presented in the listings.

5 Effectiveness Analysis Strategy

5.1 Effectiveness Endpoints

5.1.1 Primary Effectiveness Endpoint

There is no primary effectiveness endpoint for this study.

5.1.2 Secondary Effectiveness Endpoints

All secondary effectiveness endpoints will be evaluated at 36 months postoperatively.

≠ Mean change in IOP

- Change in IOP from baseline is defined as, for each subject,

$$Change = PostOp IOP - Baseline IOP$$

≠ Proportion of subjects with IOP reduction $\geq 20\%$ while using the same or fewer topical ocular hypotensive medications

The outcome of $\geq 20\%$ decrease in IOP from baseline up to 36 months post-operatively, while using the same or fewer topical ocular hypotensive medications, is determined as follows,

- Percent change in IOP from baseline is defined as, for each subject,

$$\text{Percent Change} = \frac{\text{PostOp IOP} - \text{Baseline IOP}}{\text{Baseline IOP}} \times 100$$

such that negative percent changes represent a favorable effect, while positive percent changes represent an unfavorable effect. Therefore, IOP response is achieved if the percent change is $\geq 20\%$ lower than baseline (i.e. the percentage change is $\leq -20\%$), while the subject is using the same or fewer topical ocular hypotensive medications compared to baseline.

- IOP response rate: Proportion of eyes meeting the effectiveness outcome is defined as the number of eyes with occurrence of $\geq 20\%$ decrease from baseline, while the subject is using the same or fewer topical ocular hypotensive medications compared to baseline, divided by the number of eyes having non-missing postoperative and baseline IOP measurements and non-missing postoperative and baseline hypotensive medication information.
- Combination ocular hypotensive medications will be counted as two medications. In particular, all combination medications will be programmatically counted as two medications:
 - ≠ Bimatoprost / Timolol
 - ≠ Brimonidine Tartrate / Timolol
 - ≠ Brinzolamide / Timolol
 - ≠ Dorzolamide HCl / Timolol Maleate
 - ≠ Latanoprost / Timolol
 - ≠ Travaprost / Timolol
 - ≠ Brinzolamide / Brimonidine Tartrate

Any subjects who are using the following oral medications will be excluded from the analysis of this endpoint.

- ≠ Acetazolamide
- ≠ Methazolamide
- ≠ Proportion of subjects who are not using ocular hypotensive medication with $\text{IOP} \geq 6 \text{ mmHg}$ and $\leq 18 \text{ mmHg}$

$$\text{Proportion} = \frac{\# \text{ of subjects not using ocular hypotensive medications having } 6 \text{ mmHg} \leq \text{IOP} \leq 18 \text{ mmHg} \text{ at the postoperative visit}}{\# \text{ of subjects in ITT set}}$$

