12.4 Discontinued Subjects

Subjects may be discontinued (exited) from the study early due to:

- ≠ Failure to meet protocol eligibility criteria prior to or during surgery
- ≠ Adverse event(s)
- ≠ Administrative reasons (eg, voluntary withdrawal, lost to follow-up)

Subjects who fail to meet protocol eligibility criteria prior to implantation will not be followed beyond the date of determination of ineligibility unless the reason for ineligibility is the occurrence of an adverse event. Subjects who are discontinued due to an adverse event occurring prior to implantation will be followed until resolution or stabilization of the event. Implanted subjects and subjects with failed implantation (inability to successfully deploy or insert the CyPass) will be followed until the planned end of study period.

Discontinued subjects who have been implanted or in whom implantation failed will not be replaced. Notification of a subject's early discontinuation should be made immediately to the sponsor and documented on the appropriate eCRF.

If a subject exits the study before completion of the final, planned study visit (Visit 8), the Investigator should make reasonable attempts to have the subject return to the site to perform early exit procedures. Early exit procedures are all study procedures to be conducted at Visit 8 (see Section 12.2.10).

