- v. Choroidal effusion requiring surgical drainage
- vi. Suprachoroidal hemorrhage
- vii. BCDVA loss of ≥ 2 lines from the best postoperative BCDVA

z) Elevated mean IOP ≥ 10 mmHg than the qualifying baseline mean IOP at or after 1 month postoperative

aa) CyPass device obstructed by iris, vitreous, lens, fibrous overgrowth, fibrin, or blood

bb) CyPass device malposition – positioning after deployment such that the device is not in the supraciliary space

cc) CyPass device malposition – positioning after deployment such that there is a clinical sequela resulting from device position including, but not limited to:

- i. Secondary surgical intervention to modify device position (eg, repositioning, proximal end trimming or explantation)
- ii. Corneal endothelial touch by device
- iii. Corneal edema leading to loss of BCDVA > 2 lines at the last postoperative visit, in comparison with preoperative BCDVA
- iv. Progressive ECL, defined as ongoing reduction in endothelial cell count of 30% or more relative to the screening ECD value, where ‘ongoing reduction in endothelial cell count’ is defined as losses continuing after Visit 5 (6 Month Follow-up)
- v. Erosion of device through sclera
- vi. Device obstruction requiring secondary surgical intervention

dd) CyPass device dislodgement or movement, without sequelae, where device movement is defined as a change by at least 1 in the number of CyPass rings visible that is not attributable to variations in gonioscopic viewing angle or illumination, changes in angle anatomy due to concomitant findings such as resolution of hyphema, change in anterior chamber depth, or development of focal peripheral anterior synechiae

ee) CyPass device explantation associated with CyPass placement and stability

ff) CyPass device explantation NOT associated with CyPass placement and stability

gg) Unplanned ocular surgical reintervention associated with CyPass placement and stability

hh) Unplanned ocular surgical reintervention NOT associated with CyPass placement and stability (other than paracentesis to relieve pressure prior to 1 week postoperative or Nd:YAG capsulotomy)

- ii) Significant ptosis
- jj) Atrophy/phthisis
- kk) Wound dehiscence/leak (persistent aqueous leak or fistula formation)
- ll) Subconjunctival hemorrhage
- mm) Chronic pain in the study eye present greater than 3 months postoperative
- nn) Significant foreign body sensation at or after 3 months postoperative
- oo) IOL subluxation

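### The IOP responder rules credit eyes that meet the criteria after later IOP-lowering surgery or explantation, and the 20% endpoint drops oral-drug users instead of counting them as non-responders

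*SAP*

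**What the plan says.** SAP 5.1.2 defines two responder proportions.

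- **20% endpoint.** The definition begins "IOP response rate: Proportion of eyes meeting the effectiveness outcome is defined as the number of eyes with occurrence of" a fall of at least 20% on the same or fewer topical drugs. This count is then "divided by the number of eyes having non-missing postoperative and baseline IOP measurements and non-missing postoperative and baseline hypotensive medication information". One exclusion follows, for acetazolamide and methazolamide: "Any subjects who are using the following oral medications will be excluded from the analysis of this endpoint".
- **Medication-free endpoint.** This is headed "Proportion of subjects who are not using ocular hypotensive medication with" an IOP from 6 to 18 mmHg. Its formula divides by all subjects in the ITT set.

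Protocol 8.2.1.2 lists the same endpoints and adds no condition on surgery or device status.

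Affected eyes stay in the data. The ITT set is "the set of study eyes for which a CyPass Micro-Stent implant is attempted" (SAP 2.1). Under Protocol 12.4, implanted and failed-implant subjects "will be followed until the planned end of study period". Protocol 13.1.2 anticipates explantation (items ee and ff) and unplanned reintervention (gg and hh). Item hh reads "Unplanned ocular surgical reintervention NOT associated with CyPass placement and stability", apart from early paracentesis and Nd:YAG capsulotomy. These events feed the secondary surgical intervention rates (SAP 6.3), and explantations also feed a listing (SAP 6.5.11). Neither is linked to the IOP endpoints.

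**The concern.** A responder rate in this study will be read as evidence that the device controls pressure. Protocol 7.1 itself notes that filtering surgery often lowers IOP and the need for drugs, and these are the two things the responder rules score. An eye in which the device failed and which then had filtering surgery can therefore be counted as a success. After explantation, any remaining effect of cataract surgery or of a further procedure is credited to a device that is no longer there.

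The plan is also uneven. It treats oral rescue as contaminating and surgical rescue as not. It handles oral rescue by removing the subject, so likely failures leave the denominator of the 20% endpoint.

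What is at stake is how the effectiveness summaries are read. The study is meant to give continued assurance of safety and effectiveness (Protocol 9.3, SAP 1.2). The secondary effectiveness endpoints also go into interim reports to the regulator (Protocol 15.7, SAP 1.4). There is no control arm to expose the contamination.

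**Working it through.** **Inputs from the documents.** Protocol 15.8 and SAP 7 plan 450 implanted eyes and 360 with 36-month data. Check: 360 / (1 − 0.20) = 450. I take 450 as the ITT size. The plan states no expected rate, precision or power for either IOP endpoint, so it has no figure of its own to reproduce here.

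**Inputs that must be assumed.** f is the share of observed eyes with later IOP-lowering surgery or explantation. q is the share of those that meet the responder criteria. The documents give neither.

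**Step 1: 20% endpoint against a non-responder rule.** Extra responders = 360 × f × q. Excess = 360fq / 360 = f × q.

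**Step 2: medication-free endpoint, ITT denominator.** Excess = 360fq / 450 = 0.8 × f × q. If the non-missing denominator that Protocol 15.4.2.2 describes for visit data were used instead, the excess would be f × q here too.

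| f | q | Extra responders | 20% endpoint (points) | Medication-free endpoint (points) |
|---|---|---|---|---|
| 1% | 25% | 0.9 | 0.25 | 0.2 |
| 2% | 100% | 7.2 | 2.0 | 1.6 |
| 4% | 50% | 7.2 | 2.0 | 1.6 |
| 5% | 100% | 18 | 5.0 | 4.0 |
| 10% | 100% | 36 | 10.0 | 8.0 |

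The excess is never negative. It is zero if no affected eye meets the criteria.

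**Step 3: 20% endpoint against an exclusion rule.** If the other eyes respond at rate r, the rule as written gives (1 − f)r + fq and exclusion gives r. The difference is f(q − r). With r = 60% and f = 4%, it is −1.4 points at q = 25% and +0.6 points at q = 75%. The sign is not fixed.

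**Step 4: oral-drug users, 20% endpoint only.** Let g be the share of eyes on oral drugs and r the response rate in the rest. Exclusion gives r; counting them as failures gives (1 − g)r. The difference is g × r. At an assumed g = 2% and r = 60%, it is 1.2 points.

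**Step 5: net direction of the medication-free endpoint.** SAP section 3 says "No imputations will be made for missing data", so 450 − 360 = 90 ITT eyes (20%) without 36-month data sit in the denominator as failures. Let r′ be the observed rate with affected eyes counted as non-responders, and suppose the missing eyes would have responded at r′. The reported rate is then 0.8(r′ + fq), and its difference from r′ is 0.8fq − 0.2r′. At f = 5% and q = 100% this is 4 points − 0.2r′, which is negative once r′ exceeds 20%. At r′ = 60% it is 4 − 12 = −8 points.

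**Primary test.** It uses none of these quantities. Its stated 80% power reproduces: at most 17 events in 360, exact one-sided alpha 0.0499, power 80.2%.

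**The case against.** The strongest reply is that reporting the outcome whatever happened later is a legitimate choice for an ITT set, and that the upward direction is certain only against a non-responder rule. Step 3 bears this out. But the plan never states that choice, and its exclusion of oral-drug users departs from it.

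A reader might infer that both responder rates are inflated overall. The documents do not support this for the medication-free endpoint. Its ITT denominator already scores missing eyes as failures, and Step 5 shows that this can outweigh the gap.

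A reader might also infer that the oral-drug rule distorts both endpoints. It does not. The exclusion is written under the 20% endpoint. The medication-free endpoint requires no ocular hypotensive medication at all, and the protocol treats oral agents as such (exclusion criterion 3; section 12.2.2.1), so oral users already fail it.

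Three further points stand:

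- Items gg and hh cover any unplanned ocular reintervention, so the codes alone do not identify IOP-lowering surgery.
- Failed-implant eyes are in the ITT set and can also be responders without the device. The change below does not settle that.
- The listings of IOP with medication counts, and of explantation or repositioning with date and reason, would let a careful reader find some affected eyes, but not restate the rates.

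Protocol 15.4.2.2 promises a supportive analysis in a DI set. Neither document defines that set and the SAP omits it, so it does not close the gap.

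**Conclusion.** The concern holds in a limited form. As written, SAP 5.1.2 counts qualifying eyes as responders after IOP-lowering surgery or explantation, and it removes oral-drug users from the 20% endpoint.

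Against a non-responder rule the first gap is worth f × q on the 20% endpoint and about 0.8 × f × q on the medication-free endpoint. At an assumed f of 2–5%, the upper bounds are 2–5 points and 1.6–4 points. They are reached only if every affected eye meets the criteria. The frequency is an assumption with no source in the documents.

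Taking 1% of all 450 eyes (4.5 eyes) as one point on each endpoint is tempting but wrong. The 20% endpoint divides by eyes with data, where 1% of 360 is 3.6 eyes. The same 3.6 eyes are at most 0.8 point of 450 on the medication-free endpoint.

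The endpoints carry no hypothesis (SAP 5.1.2.1) and study success rests on the primary safety rate alone. Nor would the correction isolate a device effect, since every eye also has cataract surgery and there is no control. The point concerns honest labelling of the descriptive results and is worth settling before database lock.

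**What to change.** In SAP 5.1.2:

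1. Count an eye as a non-responder in both proportions from the date of IOP-lowering surgery or CyPass explantation. Use codes ee and ff, plus those gg and hh events classified as IOP-lowering before database lock.
2. Count oral acetazolamide or methazolamide users as non-responders in the 20% endpoint. No change is needed for the medication-free endpoint.
3. Report the number of eyes affected by each rule.
4. Show mean IOP change, which has the same gap, with and without values taken after these events.
5. Keep the current rule as a sensitivity analysis.

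These are analysis rules only and leave patient management unchanged. SAP Appendix C already takes the events from the adverse event form. The cost is SAP wording, slightly lower responder rates, and a documented pre-lock classification of reinterventions. Appendix C shows no specify field for gg and hh, so that classification may need the event descriptions or site queries.
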